3.7.1.2.5. HRSD Score Over Time

HRSD score at the baseline, end of each treatment block, and end of every four week follow-up time will be tested between the two treatment groups using SAS PROC GLM at each visit. A mixed regression model will be used to test the main effects of treatment using SAS PROC MIXED across all time visits. The model will include week, treatment and treatment by week interaction adjusted for the baseline. A means model will be assumed. An unstructured covariance model will be used in the analysis. If the model fails to converge a compound symmetry covariance matrix will be assumed. The restricted maximum likelihood (REML) method will be used to estimate the covariance parameters. If the treatment by week interaction is not statistically significant then this term will be removed from the final model. The repeated factor will be visit; all other variables will be considered as fixed effects. The model is defined as follows:

$$Y_{ijk} = \mu + \tau_k + B_j + \varepsilon_{ijk}$$

where Y_{ijk} is the HRSD scores measured on k^{th} treatment and on j^{th} visit for i^{th} subject, μ is the overall mean, τ_k is the mean effect of the treatment and the interaction, B_j is the random effect, and ε_{ijk} is the error (Laird et al 1982). The sample sizes, least-squares means, and standard deviations will be presented at each visit by treatment arm for each study visit (Tables 3.7.7a-c). The assumptions relating to the mixed-effects model will be reviewed by examining residual graphs. Scatter plots of residuals will be used to examine deviations from normality and to assess lack-of-fit. The least square means (LS-means) and their standard errors at each visit will be plotted by treatment groups (Figures 3.7.3a-c).

3.7.2 Secondary Efficacy Analyses

The secondary efficacy analyses include outcome measures of Montgomery-Asberg Depression Rating Scales (MADRS), Beck Scale for Suicide Ideation (BSS), Beck Depression Inventory (BDI), Quality of Life measured by the VR-36, and Cognitive Function as measured by a neuropsychological battery.

3.7.2.1 Montgomery-Asberg Depression Rating Scales (MADRS)

An important secondary outcome variable is MADRS which is defined in Section 2.5.3.2. Higher MADRS score indicates more severe depression, and each item yields a score of 0 to 6. The overall score ranges from 0 to 60. At each time point of the baseline, end of acute treatment, and end of follow-up, mean and standard deviation of each item will be tabulated by treatment group (Tables 3.7.8a-c).

3.7.2.1.1. MADRS Score Overtime

MADRS score at the baseline, end of each treatment block, and end of every four week follow-up time will be tested between the two treatment groups using SAS PROC GLM at each visit (Tables 3.7.9a-c). A mixed regression model will be used to test the main effects of treatment using SAS PROC MIXED. The model will include visit, treatment and treatment by visit interaction adjusted for the baseline. A means model will be assumed. An unstructured covariance model will be used in the analysis. If the model fails to converge a compound symmetry covariance matrix will be

assumed. The restricted maximum likelihood (REML) method will be used to estimate the covariance parameters. If the treatment by visit interaction is not statistically significant then this term will be removed from the final model. The model is described in Section 3.7.1.2.5. The sample sizes, least-squares means, and standard deviations will be presented at each visit by treatment arm for each study visit (Tables 3.7.9a-c). The assumptions relating to the mixed-effects model will be reviewed by examining residual graphs. Scatter plots of residuals will be used to examine deviations from normality and to assess lack-of-fit. The least square means (LS-means) and their standard errors at each visit will be plotted by treatment groups (Figures 3.7.4a-c).

3.7.2.1.2. Depression Severity based on MADRS Score

According to Herrmann et al (Herrmann et al 1998), MADRS score can be categorized into four depression severity groups, i.e. normal (0-6), mild depression (7-19), moderate depression (20-34), and severe depression (>34). The severity of the depression will be tested at end of the acute treatment, and end of the following-up using proportional odds model adjusted for baseline and SAS PROC LOGISTIC will be used to run the model and p-values related to the treatment effect will be presented. Further, the generalized linear mixed model will be applied to test the differences of the proportions of subjects' remission across all the time point. The link function will be cumulative logit. SAS PROC GLIMMIX will be used to analyze the data (Tables 3.7.10a-c).

3.7.2.2 Beck Depression Inventory (BDI)

BDI is described in Section 2.5.3.3. Higher BDI score indicates more severe depression, and each item yields a score of 0 to 3. The overall score of the 21 item test ranges from 0 to 63. At each time point of the baseline, end of acute treatment, and end of follow-up, mean and standard deviation of each category will be tabulated by treatment group (Table 3.7.11 a-c).

3.7.2.2.1. BDI Score Overtime

BDI score at the baseline, end of each treatment block, and end of every four week follow-up time will be tested between the two treatment groups using SAS PROC

GML at each visit. A mixed regression model will be used to test the main effects of treatment using SAS PROC MIXED. The model will include visit, treatment and treatment by visit interaction adjusted for the baseline. A means model will be assumed. An unstructured covariance model will be used in the analysis. If the model fails to converge a compound symmetry covariance matrix will be assumed. The restricted maximum likelihood (REML) method will be used to estimate the covariance parameters. If the treatment by visit interaction is not statistically significant then this term will be removed from the final model. The model is described in Section 3.7.1.2.5. The sample sizes, least-squares means, and standard deviations will be presented at each visit by treatment arm for each study visit (Tables 3.7.12a-c). The assumptions relating to the mixed-effects model will be reviewed by examining residual graphs. Scatter plots of residuals will be used to examine deviations from normality and to assess lack-of-fit. The least square means (LS-means) and their standard errors at each visit will be plotted by treatment groups (Figures 3.7.5a-c).

3.7.2.2.2. Depression Severity based on BDI Score

According to Beck et al (Beck et al 1988), BDI score can be categorized into four depression severity groups, i.e. minimal depression (0-9), mild depression (10-18), moderate depression (19-29), and severe depression (30-63). The severity of the depression will be tested at end of the acute treatment, and end of the following-up using proportional odds model and SAS PROC LOGISTIC will be used to run the model and p-values related to the treatment effect will be presented. Further, the generalized linear mixed model will be applied to test the differences of the proportions of subjects' remission across all the time point. The link function will be cumulative logit. SAS PROC GLIMMIX will be used to analyze the data (Tables 3.7.13a-b).

3.7.2.3 Beck Scale for Suicide Ideation (BSS)

BSS is described in Section 2.5.3.4. Higher BSS score indicates higher tendency of suicidal ideation, and each item yields a score of 0 to 2. The overall score of the 21 item test ranges from 0 to 38 (last two items not counted). At each time point of the baseline, end of acute treatment, and end of follow-up, mean and standard deviation of each item will be tabulated by treatment group (Table 3.7.14 a-c). BSS

score at the baseline, end of each treatment block, and end of every four week follow-up time will be tested between the two treatment groups using SAS PROC GLM at each visit adjusted for the baseline. A mixed regression model will be used to test the main effects of treatment using SAS PROC MIXED. The model will include visit, treatment and treatment by visit interaction adjusted for the baseline. A means model will be assumed. An unstructured covariance model will be used in the analysis. If the model fails to converge a compound symmetry covariance matrix will be assumed. The restricted maximum likelihood (REML) method will be used to estimate the covariance parameters. If the treatment by visit interaction is not statistically significant then this term will be removed from the final model. The model is described in Section 3.7.1.2.5. The sample sizes, least-squares means, and standard deviations will be presented at each visit by treatment arm for each study visit (Tables 3.7.15a-c). The assumptions relating to the mixed-effects model will be reviewed by examining residual graphs. Scatter plots of residuals will be used to examine deviations from normality and to assess lack-of-fit. The least square means (LS-means) and their standard errors at each visit will be plotted by treatment groups (Figures 3.7.6a-c).

3.7.2.4. Veterans RAND 36 Item Health Survey (VR-36)

As described in the section 2.5.3.5, the VR-36 measures eight concepts of health using 12 questions with 37 items: physical functioning, role limitations due to physical health, bodily pain, general health perceptions, vitality, social functioning, role limitations due to emotional problems, and mental health. It yields scale scores for each of these eight health domains. Scoring of all eight VR-36 is based on Ware et al (1994) standard scoring algorithm, which includes a linear transformation from a raw score so that scores range from 0-100, where 100 denotes the best health. The eight scales are summarized into two components, physical and mental component summaries (PCS and MCS) and each is scored using weights derived from a national US probability sample (Ware et al 1994). The two summaries make an important contrast between the physical and psychological health status. At each time point of the baseline, end of acute treatment, and end of follow-up, mean and standard deviation of each health domain will be tabulated by treatment group (Table 3.7.16a-c).

Physical, mental and total scores at the baseline, end of each treatment block, and end of every four week follow-up time will be tested between the two treatment groups using SAS PROC GLM at each visit adjusted for the baseline. A mixed regression model will be used to test the main effects of treatment using SAS PROC MIXED. The model will include visit, treatment and treatment by visit interaction adjusted for the baseline. A means model will be assumed. An unstructured covariance model will be used in the analysis. If the model fails to converge a compound symmetry covariance matrix will be assumed. The restricted maximum likelihood (REML) method will be used to estimate the covariance parameters. If the treatment by visit interaction is not statistically significant then this term will be removed from the final model. The model is described in Section 3.7.1.2.5. The sample sizes, least-squares means, and standard deviations will be presented at each visit by treatment arm for each study visit (Tables 3.7.17a-c). The assumptions relating to the mixed-effects model will be reviewed by examining residual graphs. Scatter plots of residuals will be used to examine deviations from normality and to assess lack-of-fit. The least square means (LS-means) and their standard errors at each visit will be plotted by treatment groups (Figures 3.7.7a-c, and Figures 3.7.7d-f.).

3.7.2.5. *Cognitive Function Analysis (Neuropsychological Battery)*

Cognitive functions are assessed at screening, at the end of the acute treatment phase and at the end of the 24 week follow-up phase, including measures of executive function, attention, memory, visuospatial ability, processing speed, psychomotor function, and premorbid intelligence.

3.7.2.5.1. Self-Rating Scale Memory Function

This is an 18 item self-rating scale of memory function test which is constructed to ask subjects to compare their memory now to their memory during the period before hospitalization. For each item, subjects rated themselves on a 9 point scale from – 4 (worse than ever before), through 0 (same as before), to 4 (better than ever before). At each time point of the baseline, end of acute treatment, and end of follow-up, mean and standard deviation of each item rating scale and overall rating scale will be tabulated by treatment group (Table 3.7.18a-c). The overall scale will be analyzed at

each measurement time point using SAS PROC GLM adjusted for baseline, age, dominant hand, year of education, medical history, neurological illness, learning disability, substance abuse and test familiarity; and the mixed model will be performed to test overall scale using SAS PROC MIXED adjusted for the above covariates as well as visit. The sample sizes, least-squares means, and standard deviations will be presented at each visit by treatment arm for each study visit (Tables 3.7.19a-c). The assumptions relating to the mixed-effects model will be reviewed by examining residual graphs. Scatter plots of residuals will be used to examine deviations from normality and to assess lack-of-fit. The means (LS-means) and their standard errors at each visit will be plotted by treatment groups (Figures 3.7.8a-c).

3.7.2.5.2 Rey Auditory Verbal Learning Test (RAVLT)

The RAVLT measures a wide range of functions such as short-term auditory-verbal memory, rate of learning, learning strategies, retroactive, and proactive interference, presence of confabulation of confusion in memory processes, retention of information, and differences between learning and retrieval. Detailed method is described in Section 2.5.3.6. The test raw scores including Trials I-V, Trial B, Trial VI, Delayed recall, Recognition memory, False positives, and Trials I-V total are collected. At each time point of the baseline, end of acute treatment, and end of follow-up, mean and standard deviation of each raw score will be tabulated by treatment group (Table 3.7.20a-c). The test raw scores at each time point will be analyzed using SAS PROC GLM adjusted for baseline, age, dominant hand, year of education, medical history, neurological illness, learning disability, substance abuse and test familiarity; and the mixed model will be performed to test the each score over time using SAS PROC MIXED adjusted for the same covariates. The sample sizes, least-squares means, and standard deviations will be presented at each visit by treatment arm for each study visit (Tables 3.7.21a-c). The assumptions relating to the mixed-effects model will be reviewed by examining residual graphs. Scatter plots of residuals will be used to examine deviations from normality and to assess lack-of-fit.

3.7.2.5.3 Symbol Digit Modalities Test (SDMT)

The SDMT developed by Aaron Smith (Smith, 1991) and measuring cerebral dysfunction in children and adults, is a test for divided attention, but requires complex visual scanning and tracking, perceptual speed, motor speed, and memory. The score in the written administrations of the SDMT test is the number of correct substitutions in each 90-second interval. The total number of correct responses can be found by counting the number of responses that correctly match the number printed above each box. The score is recorded as a proportion of the total number of responses. The total score provides a measure of the speed and accuracy of symbol-digit substitutions. At each time point of the baseline, end of acute treatment, and end of follow-up, mean and standard deviation of each correct responses, total responses, and the proportion of the total number of responses will be tabulated by treatment group (Table 3.7.22a-c). The test scores at each time point will be analyzed using SAS PROC GLM adjusted for baseline, age, dominant hand, year of education, medical history, neurological illness, learning disability, substance abuse and test familiarity; and the mixed model will be performed to test the each score over time using SAS PROC MIXED adjusted for the same covariates. The sample sizes, least-squares means, and standard deviations will be presented at each visit by treatment arm for each study visit (Tables 3.7.23a-c). The assumptions relating to the mixed-effects model will be reviewed by examining residual graphs. Scatter plots of residuals will be used to examine deviations from normality and to assess lack-of-fit.

3.7.2.5.4 Trail Making Test (TMT)

TMT assesses visual attention and task switching, consisting of two parts (A and B) in which the examinee is instructed to connect a set of 25 dots as fast as possible while still maintaining accuracy. The completing time and number of errors will be collected as outcome measures for both part A and part B, and tabulated by treatment group (Table 3.7.24a-c). The test outcomes at each time point will be analyzed using SAS PROC GLM adjusted for baseline, age, dominant hand, year of education, medical history, neurological illness, learning disability, substance abuse and test familiarity; and the mixed model will be performed to test the outcomes over time using SAS PROC MIXED adjusted for the same covariates. The sample sizes,

least-squares means, and standard deviations will be presented at each visit by treatment arm for each study visit (Tables 3.7.25a-c). The assumptions relating to the mixed-effects model will be reviewed by examining residual graphs.

3.7.2.5.5. Judgement of Line Orientation (JLO)

As standardized test of visuospatial skills, JLO assesses a subject's ability to match the angle and orientation of lines in space. The 30 item test requires the examinee to match two angled lines to a set of 11 lines arranged in a semicircle and separated 18 degrees from each other. The number of total correct answers are collected and tabulated by treatment group (Table 3.7.26a-c). The test outcomes at each time point will be analyzed using SAS PROC GLM adjusted for baseline, age, dominant hand, year of education, medical history, neurological illness, learning disability, substance abuse and test familiarity; and the mixed model will be performed to test the outcomes over time using SAS PROC MIXED adjusted for the same covariates. The sample sizes, least-squares means, and standard deviations will be presented at each visit by treatment arm for each study visit (Tables 3.7.27a-c). The assumptions relating to the mixed-effects model will be reviewed by examining residual graphs. Scatter plots of residuals will be used to examine deviations from normality and to assess lack-of-fit.

3.7.2.5.6. Controlled Oral Word Association Test (COWA)

COWA test assesses subjects' verbal fluency. examinees are asked to produce as many words that begin with a specific letter (F, A, or S) as they can within one minute. The examinees are then asked to name as many animal names as possible within one minute. The test is scored for specific letter F, A, S, total of FAS (F+A+S), and animal naming in four aspects, i.e. number of correct, perservations, intrusions, and variants. The raw scores will be tabulated by treatment group (Table 3.7.28a-c). Every score at each time point will be analyzed using SAS PROC GLM adjusted for baseline, age, dominant hand, year of education, medical history, neurological illness, learning disability, substance abuse and test familiarity; and the mixed model will be performed to test the raw scores over time using SAS PROC MIXED adjusted for the same covariates. The sample sizes, least-squares means, and standard deviations will

be presented at each visit by treatment arm for each study visit (Tables 3.7.29a-c). The assumptions relating to the mixed-effects model will be reviewed by examining residual graphs. Scatter plots of residuals will be used to examine deviations from normality and to assess lack-of-fit.

3.7.2.5.7. Stroop Color and Word Test (SCWT)

SCWT assesses cognitive processing and helps diagnosis on brain dysfunction, cognition, and psychopathology. The test is based on the observation which subjects read words much faster than they identify and name colors. The Stroop Test yields three basic scores: raw word score, raw color score, and the raw color-word score. These scores will be tabulated by treatment group (Table 3.7.30a-c). Every score at each time point will be analyzed using SAS PROC GLM adjusted for baseline, age, dominant hand, year of education, medical history, neurological illness, learning disability, substance abuse and test familiarity; and the mixed model will be performed to test the raw scores over time using SAS PROC MIXED adjusted for the same covariates. The sample sizes, least-squares means, and standard deviations will be presented at each visit by treatment arm for each study visit (Tables 3.7.31a-c). The assumptions relating to the mixed-effects model will be reviewed by examining residual graphs. Scatter plots of residuals will be used to examine deviations from normality and to assess lack-of-fit.

3.7.2.5.8. North American National Adult Reading Test (NAART)

NAART estimates subjects' verbal intellectual ability. The use of a pronunciation guide is required to facilitate scoring for the NAART. If a subject pronounces a word incorrectly, put a checkmark in the "No" box and if a patient correctly pronounces a word, put a check mark in the "Yes" box on the scoring sheet. Each incorrectly pronounced word counts as one error. The total number of errors will be tabulated by treatment group (Table 3.7.32a-c). Every score at each time point will be analyzed using SAS PROC GLM adjusted for baseline, age, dominant hand, year of education, medical history, neurological illness, learning disability, substance abuse and test familiarity; and the mixed model will be performed to test the raw scores over time using SAS PROC MIXED adjusted for the same covariates. The sample sizes, least-

squares means, and standard deviations will be presented at each visit by treatment arm for each study visit (Tables 3.7.33a-c). The assumptions relating to the mixed-effects model will be reviewed by examining residual graphs. Scatter plots of residuals will be used to examine deviations from normality and to assess lack-of-fit.

3.7.2.6 Secondary Endpoint Analysis Results

The secondary endpoints are defined as severity improvements of MADRS, BSS, BDI, VR-36, and Cognitive function from baseline to end of the acute treatment. Given the several simultaneous hypothesis testing, multiplicity adjustment will be applied. The significance level for the secondary endpoint analyses will be 0.01. The analysis results can be extracted from the above analysis at the time point of end of acute treatment as shown in Table 3.7.34a-c.

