2.4.2 Secondary Outcome Variables

There are five secondary outcome measures based on their use in previous studies in major depression, where appropriate.

1. Depression measured by Montgomery-Asberg Depression Rating Scales (MADRS)
2. Suicide Ideation measured by Beck Scale for Suicide Ideation (BSS)
3. Depression measured by Beck Depression Inventory (BDI)
4. Quality of Life measured by the VR-36
5. Cognitive Function as measured by a neuropsychological battery

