2.6 Sample Size Consideration

The primary hypothesis of the study is that in VA patients with TRMD, rTMS will result in a greater remission rate at the end of acute treatment than sham rTMS. The primary outcome measure in this study is success or failure to achieve remission from depression as defined by a score on the Hamilton Rating Scale for Depression (HRSD24) of 10 or less. The primary analysis will be done as an "intent-to-treat" analysis, i.e. patients will be analyzed in the groups to which they were randomized and drop-outs will be considered treatment failures. The primary hypothesis will be addressed using a logistic regression model with PTSD diagnosis, history of substance abuse, and site as covariates. Based on review of the studies reported in the Introduction Section, the Planning Committee felt that a 10% difference between treatments would be of clinical relevance given the severity of the illness. With a sample size of 180 per group, the proposed study will have a power of 81% to detect an absolute difference between groups of 10% in the percentage of those participants who remit (6% sham and 16% rTMS). Thus, a total of 360 patients are required. This goal of 360 patients, larger than any previous study, also provides a measure of protection should some assumptions be wrong.

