3.1.2 Analysis Conventions

This section details general policies to be used for the statistical analyses. Departures from these general policies may be given in the specific detailed sections of this statistical analysis plan. When this situation occurs, the rules set forth in the specific section take precedence over the general policies. The following policies will be applied to all data presentations and analyses.

- All statistical tests will use a significance level of $\alpha = 0.05$. Two-tailed tests will be performed for all analyses that use statistical testing.
- All p-values will be rounded to 3 decimal places. All p-values that round to 0.000 will be presented as '<0.001' and p-values that round to 1.000 will be presented as '>0.999'. Any p-value $\leq \alpha$ will be considered statistically significant.
- Summary statistics will consist of the number and percentage of responses in each category for discrete variables, and the mean, median, standard deviation (SD), minimum, and maximum for continuous variables.
- All mean and median values will be formatted to one more decimal place than the measured value. Standard deviation values will be formatted to two more decimal places than the measured value.
- All percentages will be rounded to one decimal place. The number and percentage of responses will be presented in the form XX (XX.X), where the

- percentage is in the parentheses. The decimal of the percentage may be dropped due to space constraints when creating a table.
- For a continuous variable, if it is normally distributed or approximately normally distributed, Student t test and/or the general linear regression will be performed to test the group difference as proposed in the analysis plan, otherwise, Wilcoxon test and/or a quantile regression will be used as an alternative analysis method; for a categorical variable, Pearson χ^2 test and/or a corresponding generalized linear regression will be performed to test the group difference.
 - All listings will be sorted for presentation in order of treatment group, site number, subject number, and date of procedure or event.
 - All analysis and summary tables will have the population sample size for each treatment group in the column heading.
 - Calculating change from baseline to a visit will be done as follows: change = visit –baseline.

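### The flat 0.01 level for the five secondary endpoints is a valid Bonferroni cut, but the Holm procedure keeps the same 5% bound and rejects at least as many endpoints

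*SAP*

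**What the plan says.** Section 2.4.2 sets the count: "There are five secondary outcome measures based on their use in previous studies in major depression". Section 3.7.2.6 makes the same five domains the secondary family: "The secondary endpoints are defined as severity improvements of MADRS, BSS, BDI, VR-36, and Cognitive function from baseline to end of the acute treatment". It then states the intent, "Given the several simultaneous hypothesis testing, multiplicity adjustment will be applied", and the rule, "The significance level for the secondary endpoint analyses will be 0.01". No procedure is named, and no ordering, step-down or gatekeeping rule is given for these endpoints.

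The general convention in section 3.1.2 is "All statistical tests will use a significance level of" 0.05, and "Two-tailed tests will be performed for all analyses that use statistical testing". That section lets a specific section override it, so 0.01 and 0.05 do not conflict.

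**The concern.** A fixed cut holds every endpoint to 0.01 even after the others have been rejected. If four of the five reach p ≤ 0.01 and the fifth has p = 0.03, the fifth is declared negative. Holm would declare it positive, because the last threshold is 0.05 once the other four have passed, and the family-wise error would still be bounded at 5%.

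The depression, suicidal-ideation and quality-of-life measures may well move together if rTMS works, and then the fixed cut gives up the most. The endpoints at risk are those with the smaller effects, because a strongly affected scale passes either rule.

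**Working it through.** **Inputs from the SAP.** Five endpoints (2.4.2, 3.7.2.6); two-sided 0.05 in general (3.1.2); 0.01 for each secondary endpoint (3.7.2.6); 180 per group (2.6), allocated 1:1 (2.3).

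**Assumptions.** The SAP gives no secondary effect sizes or correlations. I take true standardised effects of 0.20 to 0.40 SD, correlation 0.5 between test statistics, no dropout, and one p-value per endpoint.

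**Step 1: the plan's figure.** 0.05/5 = 0.0100, an exact match. The bound is 5 × 0.01 = 0.05; for independent tests the error is 1 − 0.99⁵ = 0.0490. The level does what a Bonferroni level should do.

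**Step 2: Holm thresholds.** Order the p-values and compare them in turn with 0.05/5, 0.05/4, 0.05/3, 0.05/2 and 0.05/1, that is 0.0100, 0.0125, 0.0167, 0.0250 and 0.0500, stopping at the first failure. The first threshold equals the plan's and the later ones are larger, so any endpoint with p ≤ 0.01 is rejected under both rules. Holm can add rejections only after one endpoint has passed 0.01.

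**Step 3: power at each threshold.** The mean of the test statistic is d × √(180/2). For d = 0.30 this is 0.30 × 9.487 = 2.846. At 0.01 two-sided the critical value is 2.576, so power is Φ(2.846 − 2.576) = Φ(0.270) = 60.6%. At the five Holm thresholds in turn it is 60.6%, 63.6%, 67.4%, 72.7% and 81.2%.

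**Step 4: simulation.** 400,000 trials per scenario, correlation 0.5. Each cell reads fixed 0.01 → Holm.

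| Real effects | Power per real endpoint | All real effects confirmed | Family-wise error |
|---|---|---|---|
| 2 of 5 at 0.30 SD | 60.7% → 62.4% | 44.8% → 48.1% | 2.7% → 3.7% |
| 3 of 5 at 0.20 SD | 24.9% → 26.9% | 7.2% → 10.5% | 1.9% → 2.9% |
| 3 of 5 at 0.30 SD | 60.7% → 64.4% | 35.8% → 43.5% | 1.9% → 3.4% |
| 3 of 5 at 0.40 SD | 88.9% → 91.2% | 76.0% → 81.9% | 1.9% → 4.0% |
| 5 of 5 at 0.20 SD | 24.9% → 30.2% | 3.7% → 12.5% | no null endpoint |
| 5 of 5 at 0.30 SD | 60.6% → 70.5% | 25.9% → 50.0% | no null endpoint |
| 5 of 5 at 0.40 SD | 88.9% → 94.6% | 68.2% → 87.1% | no null endpoint |
| None | – | – | 4.2% → 4.2% |

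The chance of at least one rejection is the same under both rules in every row: for example 90.1% with five real effects at 0.30 SD and 84.5% with three. Holm rejects more endpoints in 36% and 12% of those trials respectively. In no trial did it lose a rejection that the fixed cut made.

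**Step 5: does the SAP supply five p-values?** Not yet. Section 3.7.2.4 tests three VR-36 scores (physical, mental, total). Sections 3.7.2.5.1 to 3.7.2.5.8 test about 44 cognitive scores with no composite: self-rated memory 1, RAVLT 11, SDMT 3, TMT 4, JLO 1, COWA 20, Stroop 3, NAART 1. With MADRS, BSS and BDI the count is 3 + 3 + 44 = 50, before section 3.7 repeats the secondary analyses in three populations. At 0.01 each, the bound over 50 tests is 0.50 (0.39 if independent). Holm over all 50 would start at 0.05/50 = 0.001.

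**The case against.** Four points can be made for leaving the rule alone.

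- **It is a legitimate adjustment.** The level is fixed in advance and controls the family-wise error for five tests. These are secondary outcomes of a study that section 2.3 calls phase II, and the primary test is untouched. This stands. A reader might infer that the flat 0.01 is a type I error fault for the five endpoints; the arithmetic shows that it is not.
- **The extra power is not free.** This stands too. A reader might infer that Holm costs nothing in error because both rules share the 5% bound. Only the bound is shared. With four real effects at 0.30 SD and one null endpoint, the false-positive rate on the null endpoint rises from 1.0% to 3.0%.
- **The large gain is the best case.** Moving from 26% to 50% for all five needs an equal effect on every endpoint. The SAP does not promise that: section 2.5.3.6 allows that rTMS might improve cognition or impair it. With two or three real effects, power per real endpoint rises by only about 2 to 4 points.
- **Holm needs five defined p-values.** This stands and shapes the fix. If every tested score is counted, Holm starts at 0.001 and no longer rejects everything that 0.01 rejects. The same gap undermines the flat 0.01, so it is a reason to define the family and no reason to keep the cut.

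Fixed 0.01 also gives simple matching 99% intervals, which Holm does not.

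**Conclusion.** The point holds as a matter of efficiency. On five p-values, one per endpoint, Holm at 0.05 has the same guarantee as the flat 0.01 and rejects at least as many endpoints. It does not always reject more, and it does not change the chance of a first success.

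At 0.30 SD and correlation 0.5, the gain in power per real endpoint is about 4 points if three effects are real and about 10 points if all five are. Actual family-wise error stays below 5% throughout. These sizes rest on assumed effects, correlation and full follow-up of 180 per arm. The dominance itself rests only on there being one p-value per endpoint, which the SAP has still to fix for VR-36 and cognition. The change is worth making because it is cheap and section 1.0 says that no analysis has begun; the current rule is not invalid.

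**What to change.** Replace the 0.01 sentence in section 3.7.2.6 with:

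> For each of MADRS, BSS, BDI, VR-36 and cognitive function, one deciding p-value at end of acute treatment in the ITT population (one pre-named VR-36 score and one pre-named cognitive score or composite) will be tested by the Holm step-down procedure at two-sided family-wise level 0.05. Holm-adjusted p-values will be shown in Table 3.7.34a. All other scores, and the completer and fully compliant populations, are supportive.

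The sponsor must name the VR-36 score and the cognitive score or composite in the same edit; without them neither Holm nor the flat 0.01 controls a defined family. That choice is the main work. The rest is one sentence and one procedure option in SAS, with no change to data collection, models or the primary test. The downside is that simultaneous intervals matching Holm are less simple than 99% intervals.
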